2.3.3. Exploratory outcomes

- Safety: The number of occurrences of: death, all-cause or unplanned HF hospitalisation or the requirement of iv-loop diuretics during the 6-month clinical follow-up duration
- Safety: The time to the first occurrence of: death, all-cause or unplanned HF hospitalisations or the requirement of iv-loop diuretics during the 6-month clinical follow-up duration
- Safety: The number of occurrences of acute kidney injury (defined as a 50% decline in estimated glomerular filtration rate relative to baseline, or decrease of >30 ml/min/1.73m2 and to a value below 60 ml/min/1.73m2 during the 6-month clinical follow-up duration)
- Safety: The time to the first occurrence of acute kidney injury (defined as a 50% decline in estimated glomerular filtration rate relative to baseline, or decrease of >30 ml/min/1.73m2 and to a value below 60 ml/min/1.73m2 during the 6-month clinical follow-up duration)
- Serum biomarkers (NT-proBNP, sodium, osmolality, haemoglobin, haematocrit) at 3 months after randomisation
- Weight at 3 months after randomisation
- Use of concomitant medication (diuretics in particular)

 $^{^{1}}$ The KCCQ, TDS-HF and EQ-5D-5L are scored according to 'Appendix 2: Scoring of the Questionnaires'.

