3.11. Analysis of the secondary outcomes

For the secondary parameters thirst distress, as assessed with the TDS-HF, and QoL at 3 months after randomisation, as assessed with the KCCQ-CSS, each of the KCCQ domains and the EQ-5D-5L, a similar approach as for the primary study parameters will be adopted.

The difference between groups in proportion of patients with clinically meaningful changes (defined as a difference of 5 points compared to baseline) in KCCQ-OSS and KCCQ-CSS (8, 10) and the percentage of events (death, all-cause hospitalisations, the need for iv-loop diuretics and acute kidney injury) will be tested with Chi-square or Fisher exact test, whichever appropriate. The

difference in between groups patient reported fluid intake will be analysed with a Students' t test or Mann-Whitney U test, whichever appropriate.

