3.12. Analysis of other outcomes

Time-to-event outcomes will be analysed using a Cox proportional hazards model, with, if necessary, baseline covariate adjustment in case of unexpected differences in baseline descriptive statistics. The estimated treatment effect will be presented in the form of hazard ratios with 95% confidence intervals. Kaplan-Meier plots will be used to present the pattern of events per treatment group over the follow-up period. The assumption of proportional hazards will be checked using statistical tests and graphical diagnostics based on the Schoenfeld residuals.

The exploratory safety endpoint will be assessed using a unmatched win ratio approach (16). Patients from the liberal fluid intake arm will be paired with every single patient from the standard fluid restriction arm. For each pair the better clinical outcome will be determined in the following sequential criteria and will stop after either patient has shown profit.

A 'win' is defined as the patient in the liberal fluid intake arm has the better outcome compared to the patient in the standard fluid restriction group. A 'loss' is defined in the opposite manner.

- 1. Death within 6 months follow-up
 - a. Death is worse than no death
 - b. Tied, if not possible to determine
- 2. HF hospitalisations within 6 months follow-up
 - a. More HF hospitalisations is worse
 - b. Tied, if not possible to determine
- 3. Requirement of iv-loop diuretics within 6 months follow-up
 - a. More events is worse
 - b. Tied, if not possible to determine
- 4. All-cause hospitalisation within 6 months follow-up
 - a. More all-cause hospitalisations is worse
 - b. Tied, if not possible to determine

The win ratio is: total number of wins / total number of losses.

The win difference is: percentage of wins minus percentage of loses.

4. Prespecified subanalyses

All patient characteristics of the prespecified subanalyses listed below will be presented in accordance with '3.7 Patient characteristics and baseline comparisons' of this document, unless stated otherwise.

Change of fluid management analysis

Aim:

- 1. To investigate the effect of liberal fluid intake versus fluid restriction in the subgroup of patients who were prescribed a fluid restriction prior to randomisation on the primary, (key) secondary and explorative endpoints

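### The number of safety events is listed as an exploratory outcome, but no planned analysis estimates a count or a rate

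*SAP*

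**What the plan says.** SAP section 2.3.3 separates two kinds of exploratory safety outcome. One is a number: "Safety: The number of occurrences of: death, all-cause or unplanned HF hospitalisation or the requirement of iv-loop diuretics" over the 6-month follow-up, and, as its own item, "The number of occurrences of acute kidney injury". The other is the time to the first occurrence of the same events.

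Three analyses touch these events:

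- Section 3.11 (secondary outcomes): "the percentage of events (death, all-cause hospitalisations, the need for iv-loop diuretics and acute kidney injury) will be tested with Chi-square" or Fisher's exact test. The sentence does not say whether the unit is the patient or the event.
- Section 3.12, first part: "Time-to-event outcomes will be analysed using a Cox proportional hazards model", with hazard ratios and 95% confidence intervals.
- Section 3.12, second part: "The exploratory safety endpoint will be assessed using a unmatched win ratio approach". Its tiers run from death, through HF hospitalisations ("More HF hospitalisations is worse") and iv-loop diuretics, to all-cause hospitalisations ("More all-cause hospitalisations is worse"). The summaries are the ratio of wins to losses and the difference in their percentages.

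**The concern.** An outcome defined as a number of occurrences calls for an analysis whose result is a number per patient or per unit of time, with a comparison between arms. The SAP names the outcome and then gives methods that answer other questions: who had any event, when the first one came, and which patient of a pair fared better.

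The arm under test relaxes a standard restriction. If it caused harm, some of that harm could appear as repeated admissions or repeated iv-diuretic treatment in the same patients. A first-event or any-event analysis cannot see this, and a reader of the results could not tell how many admissions per 100 patients the two policies produced.

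**Working it through.** **Step 1. Match each outcome to a method.**

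| Outcome in 2.3.3 | 3.11 chi-square/Fisher | Cox (3.12) | Win ratio (3.12) | Count or rate estimated? |
|---|---|---|---|---|
| Number of all-cause hospitalisations | any event | first event | tier 4 | no |
| Number of unplanned HF hospitalisations | not listed | first event | tier 2 (HF hospitalisations) | no |
| Number of iv-loop diuretic events | any event | first event | tier 3 | no |
| Number of AKI occurrences | any event | first event | not a tier | no |

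The win ratio stops at the first tier that separates a pair. A second HF admission therefore matters only in pairs tied on death, and an additional all-cause admission only in pairs tied on three earlier tiers.

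**Step 2. Inputs for the size.** The plan states no event rate or power for safety, so it has no figure of its own to reproduce here. Only the arm size comes from the documents: SAP 2.6 needs 454 evaluable patients, 454/0.9 = 504.4, and it enrols 506, so 506/2 = 253 per arm. The rest is assumed: a control-arm mean *m* of 0.1 to 0.3 admissions per patient in 6 months; negative binomial counts with variance *m* + *k m*² and dispersion *k* from 0 (Poisson) to 4; a true rate ratio of 1.5; complete follow-up and no deaths.

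**Step 3. One case by hand (*m* = 0.2, *k* = 2).**

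- Patients with any event: p = 1 − (1 + *km*)^(−1/*k*). Control 1 − 1.4^(−0.5) = 0.155; other arm (*m* = 0.3) 1 − 1.6^(−0.5) = 0.209.
- Share of control events that are repeats: 1 − 0.155/0.2 = 23%.
- Any-event test: z = (0.2094 − 0.1548)/√[(0.1548·0.8452 + 0.2094·0.7906)/253] = 0.0546/0.0342 = 1.60. Power = Φ(1.60 − 1.96) = 36%.
- Count test on the log rate ratio: variance = (1/0.2 + 2 + 1/0.3 + 2)/253 = 12.33/253 = 0.0487, SE 0.221, z = 0.405/0.221 = 1.84. Power = Φ(1.84 − 1.96) = 45%.

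**Step 4. Simulation over the range.** There were 10,000 trials per setting, and 1,000 for the rank test. The rank test compares counts between arms and stands in for a single win-ratio tier. Repeats are measured with equal arms; power is at rate ratio 1.5.

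| *m* | *k* | Repeats | Any event | Rank | Count | Count minus any |
|---|---|---|---|---|---|---|
| 0.1 | 0 | 4.8% | 34.4% | 34.6% | 35.4% | 1.0 |
| 0.1 | 1 | 9.1% | 29.4% | 31.1% | 31.6% | 2.2 |
| 0.1 | 2 | 12.9% | 25.9% | 26.2% | 29.4% | 3.5 |
| 0.1 | 4 | 19.3% | 20.8% | 22.5% | 25.8% | 5.0 |
| 0.2 | 0 | 9.4% | 55.9% | 59.2% | 61.5% | 5.6 |
| 0.2 | 1 | 16.6% | 44.4% | 47.3% | 52.6% | 8.2 |
| 0.2 | 2 | 22.6% | 35.8% | 36.2% | 45.7% | 9.9 |
| 0.2 | 4 | 31.8% | 25.6% | 25.8% | 36.2% | 10.6 |
| 0.3 | 0 | 13.6% | 71.6% | 78.1% | 78.9% | 7.3 |
| 0.3 | 1 | 23.1% | 51.4% | 59.7% | 64.7% | 13.3 |
| 0.3 | 2 | 30.1% | 40.7% | 45.4% | 55.5% | 14.8 |
| 0.3 | 4 | 40.4% | 27.4% | 30.3% | 43.3% | 15.9 |

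With equal arms, the any-event test rejects in 4.7% to 5.3% of trials and the count test in 4.7% to 5.5%, so both are valid. Over *k* = 1 to 4 the count test gains 2 to 16 points over the any-event test and 0.5 to 13 points over the rank comparison. The rank figures carry simulation error of about 3 points.

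**The case against.** Four points can be made for the plan.

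1. *The win ratio already uses counts.* This is true for three of its four tiers, with the patient as the unit. A reader might infer from 3.11 that chi-square is the only analysis of these events; 3.12 shows that it is not. What remains is that the win ratio returns no event rate or rate ratio and has no AKI tier.

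2. *Section 3.11 concerns patients, not events.* A reader might take its wording literally, treat repeat admissions as independent, and conclude that the false-positive rate is inflated. The documents do not support that reading. The same sentence begins with proportions of patients, section 3.2 counts patients with at least one event (for the interim reports), and the draft results table in Appendix 1 lists these events under the number of patients per arm. Read this way the test holds its level. Stating the unit would help, but its absence is only a missing detail.

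3. *A recurrent count may never have been meant.* The matching objective in 2.1.3 speaks of the (time to first) occurrence, and death, which cannot recur, is in the list. The number of occurrences could therefore mean the number of patients affected. This cannot be excluded. Against it, 2.3.3 sets the number apart from the time to first event, and the win ratio counts repeats, so repeats are of interest and will be available.

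4. *The outcomes are exploratory and power is low in any case.* This stands. The count test exceeds 70% power in only one of the 12 settings, and every rate in the table is assumed.

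**Conclusion.** The point holds in a limited form. Section 2.3.3 names numbers of occurrences as outcomes, and nothing in 3.11 or 3.12 estimates one. For AKI the gap is widest, because only the percentage test and the first-event model apply to it. None of the planned analyses is invalid, no type I error problem is shown, and the primary and key secondary conclusions are untouched.

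What is lost is a direct description of event burden and some sensitivity to harm. The loss is 2 to 16 percentage points of power against the any-event test if counts are overdispersed, and 1 to 7 points if they are Poisson. These figures rest on the assumed rates, dispersion and rate ratio, and they ignore deaths and incomplete follow-up. If the sponsor meant numbers of patients and not of events, rewording 2.3.3 would close the inconsistency, but the event burden would still go unestimated. This is a cheap improvement, not a defect that threatens the trial.

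**What to change.** Keep the chi-square/Fisher test, stated as applying to patients with at least one event, and keep the Cox models and the win ratio.

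Add to 3.12: the per-patient numbers of all-cause hospitalisations, unplanned HF hospitalisations, iv-loop diuretic episodes and AKI occurrences will each be analysed by negative binomial regression (or Poisson regression with robust standard errors), with arm as factor and log observed follow-up time as offset. Report the rate per arm and the rate ratio (liberal versus restricted) with 95% CI, with the number of deaths per arm beside them.

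The cost is a paragraph of SAP text and four model runs. The win ratio already needs the first three kinds of count. For AKI, a rule for what counts as a separate episode has to be written, since the definition in 2.3.3 only compares with baseline. The downside is that death ends the count, so the rate ratio must be read together with mortality. An arm with more early deaths could otherwise appear to have fewer admissions.

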2.1.2. Secondary objectives

To investigate the effect of liberal fluid intake versus standard fluid restriction (1500 ml/day) on:

- Thirst distress at 3 months after randomisation, as assessed with TDS-HF
- QoL at 3 months after randomisation, as assessed by KCCQ Clinical Summary Score (-CSS), each of the KCCQ domains and the proportion of patients with clinically meaningful changes in these scores, and the European Quality of Life Five Dimensions Five Levels questionnaire (EQ-5D-5L)
- Patient reported fluid intake at week 6
- Safety, as assessed by the composite of: death, all-cause hospitalisation and the requirement to apply iv-loop diuretics during the 6-month clinical follow-up duration.

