2.3. Outcomes

2.3.1. Primary outcome

• QoL as assessed by KCCQ-OSS¹ at 3 months after randomisation

2.3.2.Secondary outcome

Key secondary outcome:

• Thirst distress as assessed by the TDS-HF¹

Other secondary outcomes:

- QoL at 3 months as assessed by KCCQ-CSS
- QoL at 3 months as assessed by each of the KCCQ domains and the proportion of patients with clinically meaningful changes in these scores
- QoL at 3 months as assessed by EQ-5D-5L¹
- Patient-reported fluid intake in week 6
- Safety: The composite clinical endpoint: death, all-cause hospitalisation and the requirement of iv-loop diuretics during the 6-month clinical follow-up duration

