3.2. Interim analyses

The DSMB will perform two interim analyses, when data are available, of 33% and 66% of the patients for safety concerning the occurrence of death, HF hospitalisations and acute kidney injury.

The objective of the interim analysis will be to assess the following:

- Safety: is there any difference in the safety profile between treatment groups?
- Are there any other observations in the accumulated data that should be communicated to the sponsor?

The following will be the main parameters of interest for the DSMB:

- The occurrence of HF hospitalisations
- The occurrence of death
- The occurrence of acute kidney injury

All appropriate safety measures will be summarized for the safety population by treatment for the treatment period. Safety measures will be reported per treatment group, the number (n) and percentage (%) of patients experiencing at least one event. The denominator for computation of percentages is the safety population within each treatment group.

There are no interim analyses for efficacy.

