3.3. Multiplicity adjustment

The primary and key secondary endpoints will be tested hierarchically. Other secondary endpoints will be considered supportive only and there will no corrections for multiple testing.

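### The secondary 6-month safety outcome gets only a chi-square or Fisher test, with no effect estimate or confidence interval tied to the safety objective

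*SAP*

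**What the plan says.** SAP 2.1.2 lists as a secondary objective "Safety, as assessed by the composite of: death, all-cause hospitalisation and the requirement to apply iv-loop diuretics" over 6 months, and SAP 2.3.2 repeats it as a secondary outcome: "The composite clinical endpoint: death, all-cause hospitalisation and the requirement of iv-loop diuretics during the 6-month clinical follow-up duration".

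The analysis is in SAP 3.11, where the "percentage of events (death, all-cause hospitalisations, the need for iv-loop diuretics and acute kidney injury) will be tested with Chi-square or Fisher exact test". That sentence lists the components and acute kidney injury (AKI) without naming the composite. The draft outcome table in SAP Appendix 1 has a composite row and a P value column, so I take the same test to apply to it. No effect measure or interval is named for these outcomes.

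Elsewhere the plan does ask for estimates. SAP 3.10.1 promises a point estimate and 95% confidence interval for KCCQ-OSS, and 3.11 extends a similar approach to TDS-HF, the other KCCQ scores and EQ-5D-5L.

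Among the exploratory outcomes, SAP 2.3.3 includes "The time to the first occurrence of: death, all-cause or unplanned HF hospitalisations or the requirement of iv-loop diuretics", and separately time to first AKI. For time-to-event outcomes, SAP 3.12 states: "The estimated treatment effect will be presented in the form of hazard ratios with 95% confidence intervals". It allows baseline covariates to be added if unexpected baseline differences appear.

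SAP 2.6 sizes the trial on KCCQ-OSS and adds a power statement for thirst distress. Neither document gives an event rate, a margin or a power statement for the clinical events.

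**The concern.** Liberal intake is the investigational arm and restriction is standard practice (SAP 2.4). A quality-of-life gain is therefore useful only alongside a credible statement about harm.

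A chi-square or Fisher test addresses the null hypothesis of equal event percentages. A small p value can show harm. A large one does not separate a true absence of excess risk from too few events to see it. An interval does, because its upper limit is the largest excess that the data have not ruled out. As written, the secondary safety outcome has the test without the interval, in a trial that was not sized for events.

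**Working it through.** **Inputs from the documents.** Difference 2.5 points, SD 20, correlation 0.88, alpha 0.05, power 80%, 454 evaluable, 10% drop-out, 506 enrolled (SAP 2.6); 1:1 allocation (SAP 2.5). This gives 253 per arm enrolled, or 227 per arm evaluable.

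**Assumptions.** The control risk at 6 months is not stated, so a range is shown. The sidedness of the safety test is not stated either, and two-sided 5% is assumed. The 1.5-fold rise is a yardstick, not a margin from the plan.

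**1. The plan's own figure.** The ANCOVA residual SD is 20 × √(1 − 0.88²) = 9.50. Then n per arm = 2 × (9.50 × (1.960 + 0.842) / 2.5)² = 226.65, rounded up to 227, so 454 in total. Next, 454 / 0.9 = 504.4, so 505, raised to 506 for equal arms. The stated size is reproduced, and it contains no event-based input.

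**2. Power of the planned tests for a 1.5-fold rise.** Exact enumeration of two binomials gives the following (chi-square without continuity correction / Fisher). The miss rate is 100% minus power.

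| Control v liberal risk | 253 per arm | 227 per arm |
|---|---|---|
| 5% v 7.5% | 21% / 17% | 19% / 15% |
| 10% v 15% | 40% / 35% | 37% / 32% |
| 15% v 22.5% | 58% / 54% | 54% / 49% |
| 20% v 30% | 74% / 71% | 69% / 66% |
| 25% v 37.5% | 86% / 84% | 82% / 80% |

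At 253 per arm, the chi-square test thus misses the rise in 79% of trials at 5% control risk, 60% at 10%, 42% at 15%, 26% at 20% and 14% at 25%.

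**3. Where power crosses 50%.** In the normal approximation, power is 50% when 0.5p√n = 1.96 × √(2 × 1.25p × (1 − 1.25p)). Squaring and solving gives p = 9.60 / (0.25n + 12.00).
- n = 253: 9.60 / 75.25 = 12.8%.
- n = 227: 9.60 / 68.75 = 14.0%.

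The same approximation, solved numerically for 80% power, gives about 22% (253 per arm) and 24% (227 per arm). Fisher's test needs slightly higher risks.

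**4. What an interval would show if both arms had the same observed risk p, 253 per arm.** The upper limit of the risk ratio is exp(1.96 × √(2(1 − p) / (pn))). The half-width of the risk difference is 1.96 × √(2p(1 − p) / n).

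| Observed risk, both arms | Upper 95% limit, risk ratio | Half-width, risk difference |
|---|---|---|
| 5% | 2.14 | 3.8 points |
| 10% | 1.69 | 5.2 points |
| 15% | 1.51 | 6.2 points |
| 20% | 1.42 | 7.0 points |
| 25% | 1.35 | 7.5 points |

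At 10%, for example, √(2 × 0.9 / (0.1 × 253)) = 0.267 and exp(1.96 × 0.267) = 1.69. So even with no observed difference, a 1.5-fold increase is excluded only when the risk is a little above 15%.

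**The case against.** Four points on the other side deserve weight.

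- **An interval already exists in the SAP.** A reader might infer that the plan puts no bound at all on excess risk. That is not so: 3.12 gives a hazard ratio with a 95% interval for time to first occurrence of essentially the same events, and for AKI. What remains is that this analysis is exploratory and nothing ties it to the secondary objective.
- **Low power is not established.** A reader might infer that the test usually misses a 1.5-fold rise. The documents give no event rate. The composite includes all-cause hospitalisation over 6 months, so its risk could lie on either side of 13% to 14%. No component can be more frequent than the composite, so low power is more plausible for the components, but their rates are not given either.
- **The plan does not equate non-significance with safety.** A reader might infer that it does. No sentence says so. SAP 3.3 says "Other secondary endpoints will be considered supportive only and there will no corrections for multiple testing", and the question "is there any difference in the safety profile between treatment groups" in SAP 3.2 belongs to interim monitoring by the DSMB. The supportive label concerns multiplicity, however, and does not remove the need to estimate harm.
- **The draft table proves little.** Appendix 1 says the tables may change. The KCCQ-OSS row has the same layout, although an interval is promised for it in 3.10.1. Readers could also compute an interval from the arm counts. The gap therefore rests on the text of 3.11, not on the table.

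Finally, the SAP cites protocol version 4.2, while the supplied protocol file is a response letter to a journal. An event-rate assumption or margin in the full protocol cannot be ruled out.

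**Conclusion.** The point holds as a gap in SAP 3.11. The secondary safety outcome has a test of difference and no effect estimate or interval, and the exploratory hazard ratio in 3.12 is not connected to it.

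Its size is conditional. Under a two-sided 5% chi-square test, a 1.5-fold rise is more likely missed than found only if the control risk is below about 13% (253 per arm) or 14% (227 per arm). Above that the test finds it more often than not, though with less than 80% power until about 22% to 24%. The documents do not say which side applies. The case for an interval does not depend on the answer, because a test of equality does not bound harm at any event rate. This is a worthwhile, inexpensive improvement, and does not affect the primary analysis.

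**What to change.** **In SAP 3.11**
- For the 6-month composite, named explicitly, and for each component and AKI, report the risk difference and risk ratio with 95% confidence intervals.
- Alongside, report the hazard ratio (95% CI) from a Cox model without data-driven covariate adjustment. The clause in 3.12 that allows covariates after unexpected baseline differences should not govern this result.
- Add a rule such as: *The safety conclusion will rest on the upper 95% confidence limit, reported as the largest increase not excluded by the data. A p value of 0.05 or more will not be interpreted as evidence of no difference in safety.*

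**In SAP Appendix 1**
- Add an effect (95% CI) column to the safety rows of the outcome table.

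**Cost.** A few sentences and one column, using data already collected. No margin, extra patients or fixed detectable-excess figure is needed. The change does not raise power; it makes the remaining uncertainty visible. The downside is a less favourable safety statement, because a moderate increase will probably not be excluded.
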